The sample consists of 96 children with bilateral hearing loss and one of their caregivers (mother, father, grandparent). Children of all races and genders will be included in the sample. All children will be between 12 and 18 months of age) at the start of the study. Children will have a diagnosis of bilateral hearing loss. This age was chosen for several reasons. First, this is the age at which intentional communication usually emerges and prelinguistic communication skills develop. As such, this age is necessary to study the effects of early intervention on prelinguistic skills for young children with hearing loss. Second, children are typically seen for an audiology visit during this time, so it is an easy time to enroll study participants. Third, the majority of children are wearing hearing aids at this time. Fourth, 12 months is an age when we are able to test developmental processes that may influence response to intervention. Fifth, parents may be more likely to participate in research when their baby is older and after they have had time to process the diagnosis. Children will start the study around 12-18 months of age and continue in the study for 24 months.

Given a sample size of 86 (96 recruited participants with 10% attrition), we project greater than 99% power for main effects of the intervention (Aim 1) as large as those shown in our pilot study (d=1.07) (see Justification and Feasibility in Research Strategy). We further project 80% power for effects as low as d=.61 and 90% for d=.71. Each of the three previous estimates assume control for pre-test and 10% attrition (e.g., n=86). Our research group has maintained greater than 95% retention in comparable studies over the last two years. We would retain power for smaller effect sizes of d=.58 (80% power, down from d=.61) and d=.67 (90% power, down from d=.71) if no attrition occurs.

5.0 Research Locations:

All study procedures will occur in the homes of participants or at the Early Intervention Research Group at Northwestern University under the supervision of the principal investigator ([name]). Video conferencing services (such a zoom) will be used for all sessions, with the exception of "baseline only" activities and "eye tracking" activities.

Page 3 of 20 Revised: May 25, 2018

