Parent Interview	answers 35 questions about how their child responds to different auditory stimuli such as music or distant sounds) Demographics Survey (the parent answers questions about demographic information such as occupation, level of education, family members living in the home). Communication Decision Making – Survey about parent's believes about communication Intervention surveys - Questionnaire for the treatment group about their expectations and experiences with the research intervention. CSBS parent questionnaire – Asks for parent report of child communication. Cognitive survey – There will be one standardized cognitive development survey to gather information about cognition at two timeponits. The Ages and Stages questionnaire - ASQ (standardized) at TO and the Parent Report of Children's Abilities - PACA (standardized) when the child is 24 months old. Parent Feedback about research – Survey asking parents for feedback about experience after major timepoints ASD screening survey – Survey asking parents about common behaviors associated with ASD. Completed when child is 20 months and 24 months old. This is completed by the parent to inform the clinical team if the parent has some developmental concerns about their child. Exit Survey (T24 only) – Gather thoughts from the family about their participation and preferences. The Deaf Language Exposure Assessment Tool (the parents report on language exposure across the day by different speakers. The number of questions depends on the number of language and number of speakers. The number of questions depends on the number of language and number of speakers. (Video/Phone Interview)	DLEAT (60 mins) Video call	Pre (T0) When child is 24 months old When Child is 36 months old Follow-up (T24) – only if child is older than 38 months old at study
	Receptive-Expressive Emergent Language	REEL (30	exit Pre (T0)
Parent Interview	Scale-3 (REEL-3) parent report	mins)	Post (T7)

			Video call		
Parent Surveys/Interviews (for children without hearing loss)	The MacArthur-Bates Communicative Development Inventories (MCDI): Words and Gestures or Words and Sentences (the parent selects which words their child says and understands out of 680 words) Demographics Survey (the parent answers questions about demographic information such as occupation, level of education,	Parent	Surveys (40 mins)	Home	Pre (T0)

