Monthly Doront	family members living in the home). The MacArthur-Bates Communicative Development Inventories (MCDI): Words and Gestures or Words and Sentences (the parent selects which words their child says and understands out of 680 words). English, Spanish, and American Sign Language versions (if applicable) Use of Community-Based Intervention	Parent	60 min.	Home	Monthly
Monthly Parent Surveys/Interviews	Services and Hearing Device Log (the parent answers questions about how many and what types of other therapy services their child received in the last month; indicates how often the child wears their hearing device across 8 different routines, such as meal times) Child's Communication – Survey about				
Visual Reception scale of the Mullen Scales of Early	child's communication The child is presented with different nonverbal tasks such as looking for a ring under a washcloth until the child fails to complete	Child	20 min.	Home or Lab	Post (T24)
Learning (MSEL) Goldman-Fristoe Test of Articulation – 3 rd edition (GFTA-3)	three consecutive tasks correctly. The GFTA-3 will take 20 minutes to administer. The GFTA-3 measures phonological skills by assessing an individual's articulation of the consonant and consonant cluster sounds of Standard American English. It provides information about an individual's speech sound ability by sampling both spontaneous and imitative sound production in single words and connected speech. GFTA-3 provides age-based normative scores separately for females and males for the Sounds-in-Words and Sounds-in-Sentences tests. Intelligibility is reported as a percentage score, and Stimulability information is reported in table format.	Child	20 min.	Home or Lab	Follow-up (T24)
Attention to Speech vs Sine-Wave Eye- Tracking Task	Children will be presented with two types of trials: speech sounds, and sinewave-transformed complex sounds. Once the child is attending to the screen, a trial will begin. Children will see either a red and white checkerboard pattern or a red and white bullseye. On speech trials, children will hear a random sequence of syllables ("lif" and "neem"). On sinewave trials,	Child (Chicagolan d participants only)	5 min.	Lab (if allowed by the state)	Pre (T0)

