Parent Use of Communication Support Strategies	Latent	Parent use of communication support strategies coded from a parent-child interaction	The following measures from the coded parent-child interaction sample: Percentage of intervals in which the adult is	Monthly from 12 to 18 months of age (6 time points between pre and post)	Analysis 1.1: Dependent Analysis 2.1: Dependent Analysis 4.1a: Mediator Analysis 4.1b: Mediator
			communicating within the child's line of sight Percentage of adult communication that is paired with a gesture in the child's line of sight Percentage of intervals in which the adult's play is related and is in close proximity to the child Percentage of child nonverbal actions that are mirrored and mapped Percentage of child communication that is followed by a contingent response Percentage of adult communication that is in response to child communication Percentage of adult communication Percentage of adult communication that contains a child linguistic target Percentage of child communication to which the adult imitates and adds a word	Monthly from 18 to 36 months of age (18 time points between post and follow-up)	Analysis 3.1: Dependent Analysis 4.2a: Mediator Analysis 4.2b: Mediator
Child Prelinguistic Communicative Acts	Latent	Language Sample	Number of child prelinguistic communicative acts coded from the language sample	12 to 18 months of age (6 time points between pre and post)	 Analysis 1.2a: Dependent Analysis 2.2a: Dependent Analysis 2.3a: Dependent Analysis 4.1a: Dependent Analysis 4.3a: Mediator
Child Overall Prelinguistic Skills	Observed	Communication and Symbolic Behavior Scale (CSBS)	Total Scaled Score	At 18 months of age (post)	 Analysis 1.2b: Dependent Analysis 2.2b: Dependent Analysis 2.3b: Dependent Analysis 4.1b: Dependent Analysis 4.3a: Mediator Analysis 4.3b: Mediator
Child spoken words	Latent	MacArthur-Bates Communicative Development Inventory; Language Sample	Total number of Words Said from the MacArthur- Bates Communicative Development Inventory Total number of different spoken word roots from the language sample	18 to 36 months of age (18 time points between post and follow-up)	 Analysis 3.2a: Dependent Analysis 4.2a: Dependent Analysis 4.3a: Dependent
Child overall spoken language	Observed	Preschool Language Scale-5 th Edition	Total Standard Score	At 36 months of age (follow-up)	Analysis 3.2b: DependentAnalysis 4.2b: DependentAnalysis 4.3b: Dependent

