Multicollinearity. This proposal includes a large set of prelinguistic and linguistic variables, some of which will be included in the same analyses. Our data reduction is one part of our solution to multicollinearity, such that latent constructs that account for shared variation between comparable predictors will be used when possible. In other cases, we will control for multiple collinear variables in the same analysis, specifically when using multiple coded variables from naturalistic parent-child interactions. In those cases, we will use alternative decomposition and transformation methods. Principle components analysis (PCA) can transform a set of collinear predictors into a set of uncorrelated variables representing variance in the original data. For example, a simple PCA of one parent and one child variable would yield two components: one indicating shared family level behavior and the other representing scaled differences between parent and child. We will further explore non-linear transformations to make sure non-linear associations and distributional assumptions are accounted for, including both simple (e.g., polynomial or logarithmic transformations to improve distributions) and complex (e.g., adjusting observed child communication for proportion of time spent communicating) transformations. This set of methods integrates well within our SEM framework and multivariate longitudinal design.

Missing data. Given this is an intent-to-treat trial, all 96 children randomized will be included in the analyses of primary outcomes even if data are missing. However, our preliminary studies showed high retention rates (e.g., 95% retention in the pilot study - R03DC012639), but missing data occurs in all longitudinal studies. All models will be estimated using full information maximum likelihood (FIML), which uses all available data and yields unbiased parameter estimates under the most common missingness mechanisms. We will further use our set of predictors and covariates to predict missingness, and include those variables as covariates to conform to FIML assumptions. For non-ignorable missing data, we will conduct sensitivity analyses using non-ignorable pattern-mixture and selection models to investigate the robustness of our conclusions across the different models for missing data.

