Analysis 3.2a. Intervention will predict the slope factor in a latent growth curve model of child spoken language outcomes (a latent variable of total number of different words said from the MCDI and total number of different spoken words from a language sample) from 18 months (post) to 36 months of age (follow-up). This will be accomplished by including intervention as a predictor in the child spoken word growth curve.

Analysis 3.2b. Intervention will predict PLS-5 Standard Scores at 36 months via multiple regression. We will test PLS-5 Standard Scores controlling for pre-test scores as we did in Analysis 1.2b.

Aim 4 Analyses

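### One of the two spoken-words indicators cannot exceed 680 words, and the SAP has no ceiling handling, so the 3.2a slope difference is distorted if many children near the maximum

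*SAP*

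**What the plan says.** SAP Table 1 lists child spoken words as a latent construct measured monthly from post-test to follow-up. It takes two variables: "Total number of Words Said from the MacArthur- Bates Communicative Development Inventory" and "Total number of different spoken word roots from the language sample". The construct is the dependent variable in Analyses 3.2a, 4.2a and 4.3a.

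For Analysis 3.2a the SAP states: "Intervention will predict the slope factor in a latent growth curve model of child spoken language outcomes". It fixes no curve shape and names no censored or bounded model.

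Protocol section 8.0, Table 1, describes the MCDI, at the major time points and in the monthly surveys, as a form in which "the parent selects which words their child says and understands out of 680 words".

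On age, protocol section 4.0 says: "Children will start the study around 12-18 months of age and continue in the study for 24 months". SAP Table 1 labels the window as 18 to 36 months of age, but the protocol foresees later exits: its last language-exposure interview is set at T24 "only if child is older than 38 months old at study" exit.

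The nearest thing to a safeguard is under Multicollinearity in the SAP: "We will further explore non-linear transformations to make sure non-linear associations and distributional assumptions are accounted for". The Latent Growth Curve Modeling section adds that such curves can be extended to nonlinear change, without committing 3.2a to that.

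**The concern.** Once every word on the list is ticked, a child's MCDI score stays at 680 however many more words are learned. A growth model for a continuous outcome reads that as zero growth on this indicator. If one arm is ahead in level or grows faster, it meets the maximum sooner and more often, so flattening is unequal between arms and enters the slope difference that 3.2a tests.

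Nothing planned separates children tied at the maximum:

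- A monotone transformation leaves ties tied.
- A curve that bends cannot tell a full list from slowed learning.
- Full information maximum likelihood deals with missing values, and a capped score is an observed value.
- The item factor analysis described for data reduction handles categorical items, but Table 1 extracts a total.

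Analysis 3.2a is a long-term child efficacy analysis, and 4.2a and 4.3a reuse its slope as the outcome of a mediation path. The main stake is the size, and in one scenario the sign, of the estimated effect on word growth.

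**Working it through.** **Ages and occasions (protocol 4.0 and 8.0).** Age at T24 is 12 + 24 = 36 to 18 + 24 = 42 months. Age at T7 is 12 + 7 = 19 to 18 + 7 = 25 months. T7 to T24 gives 24 - 7 + 1 = 18 monthly occasions.

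**The plan's own power figures.** With two-sided alpha .05 and equal arms (both assumed, since the SAP states neither), a two-sample t-test reproduces the pre-post figures. With n = 86, power is 79.8% at d = .61 and 90.2% at d = .71. With n = 96 it is 80.3% at d = .58 and 90.1% at d = .67. The growth-curve figures (80% at d = .34, 90% at d = .45) are the ones that concern 3.2a. They cannot be reproduced, because the variances of intercept, slope and residual and the scale of d are not given. The power section mentions no upper bound on any outcome.

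**Size of the distortion.** Neither document gives word counts by age, so all of the following inputs except the cap and the number of occasions are assumptions:

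- T7 words: mean 80, SD 70.
- Linear growth to a mean M at the last visit, so mean slope = (M - 80)/17 words per month, with slope SD = 40% of that and residual SD 25.
- Treated mean slope higher by d slope SDs, with d = .34 or .61.
- MCDI clipped at 680.
- Word roots = 0.15 x true words plus noise with SD 12, with no cap.
- Outcome: each child's least-squares slope over 18 visits, for the MCDI alone and for an equal-weight composite of the two standardised indicators, as a stand-in for the latent variable.

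Example with M = 600 and d = .61: mean slope = 520/17 = 30.6, slope SD = 12.2, true slope difference = .61 x 12.2 = 7.5 words per month. After clipping, the simulated MCDI slope difference is about 4.5, or about 61% of the uncapped one.

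Share of the slope difference that is kept:

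| M | Controls at 680, last visit | MCDI alone, equal start | Composite, equal start | Composite, treated 0.5 SD ahead at T7 |
|---|---|---|---|---|
| 200-300 | about 0% | 100% | 100% | 100% |
| 400 | 3% | 97-98% | 98-99% | 97% |
| 500 | 16% | 83-86% | 91-93% | 86% |
| 600 | 36% | 61-66% | 80-83% | 71-72% |
| 700 | 53% | 40-46% | 70-72% | 57-60% |
| 800 | 66% | 24-30% | 62-64% | 48-52% |

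**Power** (N = 96, d = .61). At 36% capped with equal starts, composite power moves from about 84% to 81%, because the cap also shrinks the slope SD. With a treated head start of 0.5 SD (0.5 x 70 = 35 words) it falls from about 85% to 75%.

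**Sign.** With equal true slopes and the same head start, the MCDI slope difference turns negative: -0.17 words per month at 16% capped, rising in size to -1.48 at 66%. On the composite the corresponding standardised difference is small, at most about -0.06.

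**No arm difference.** With equal levels and equal slopes, the cap creates no bias.

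**The case against.** The strongest reply is that the problem is hypothetical. The documents give no word counts, and the protocol's background section says that children with hearing loss are slow to reach their first 50 words and have poorer vocabulary. If the mean at the end of follow-up is 200 to 400 words, at most 3% of controls are capped and the loss is 0-3%. That stands, and it makes the point conditional. It does not remove it: the same section stresses wide variability, and the plan has no step that would reveal the share at the maximum.

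A reader might infer that capped children are scored as having stopped growing, so that the 3.2a effect is certain to be understated. The documents do not support this. The outcome has a second indicator without this cap, which can still rise. Understatement also needs many children near the maximum and a real arm difference, and neither can be established here. Nor is attenuation the only possible direction.

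A reader might also compare arms on the MCDI alone at the last visit. With control means of 450-650, SD 200-250, d = .61 and 43 per arm, 13-45% of controls and 29-69% of treated children sit at 680, only 80% down to 43% of the difference remains, and power drops from 80% to 77-62%. That is not Analysis 3.2a, which uses 18 occasions and two indicators, and the assumed means are high. At a mean of 300 with SD 150-200, the same formula keeps 94-99%.

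Finally, Analysis 3.2b (PLS-5 at follow-up) is untouched by the 680 limit, so long-term child efficacy does not rest on 3.2a alone. That also stands.

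**Conclusion.** The point holds in conditional form. The documents establish the 680-word bound, the indicator's role in 3.2a, 4.2a and 4.3a, follow-up to 36-42 months, and the lack of ceiling handling. The size of the harm is not established. Under the stated assumptions it runs from nothing, through 17-20% of the slope difference on the composite with 36% of controls capped (28-29% if treated children start T7 half an SD ahead), to more at higher shares. The word-roots indicator offsets part of the loss but not all of it. The damage is mainly to the estimate; power changes little unless treated children are already ahead at T7. These figures rest on assumed word counts, linear growth and equal weights. The latent model's real loadings are not given and could shift them either way.

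**What to change.** Keep the two-indicator growth model as the main analysis of 3.2a. Add to the SAP, before outcomes are examined by arm:

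- A table of the share of children at 680, and near it by a stated threshold, by month and arm.
- A ceiling-robust supporting analysis for 3.2a and for the spoken-words slopes in 4.2a and 4.3a: a right-censored (or bounded-count) growth model for MCDI Words Said, and a separate growth model for word roots.
- A rule that the 3.2a conclusion is qualified if these differ from the main model in direction or materially in size.

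A supporting role is proportionate. A censored indicator as the only main model, inside a curve-of-factors model with 18 occasions and 86 to 96 children, may not converge.

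The cost is SAP wording and extra model fitting, with no new data. The downside is that the censored model relies on a distributional assumption above the cap that the data cannot check. If few children reach the maximum, the results will barely change and the table will show it.

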6.0 Multiple sites: NA

7.0 Reliance Agreements/Single IRB: [name], [name], and [name] have Individual Investigator Reliance Agreements on this IRB.

[figure not shown]
8.0 Procedures Involved:

This study will use a parallel stratified randomized clinical trial design with repeated measures to examine the effects of a parent-implemented communication treatment (PICT) on parent use of communication support strategies and on pre-symbolic communicative acts and spoken language outcomes for children with HL. Children and their caregivers will be randomized to either PICT or a business-as-usual (BAU) control group. Children assigned to the PICT group will receive weekly, hour-long intervention sessions in their homes for 6 months. Parents and children will be assessed prior to intervention (at baseline, T0, pre), immediately after intervention (at T7, 7 months after baseline, post), 18 months after intervention (at T24, 24 months after baseline, follow-up), and monthly using abbreviated measures for the entire study (T0 – T24).

Parent-child dyads will be randomized individually following phone screening, completion of baseline assessments, and determination of hearing device status and communication mode. Randomization will be stratified by hearing device status (hearing aid or bone conduction device, cochlear implant) and communication mode (spoken only, sign + spoken). Given that hearing profiles will likely vary among participants, we chose to use hearing device as a stratification factor because it is categorical (hearing aid/bone conduction device or cochlear implant). Children who are a cochlear implant candidate will be assigned to the cochlear implant stratum. In addition, a child with one hearing aid and one cochlear implant will be assigned to the cochlear implant stratum.

Parents in both the intervention and BAU control groups will continue to receive early intervention services according to their individualized family service plan. Figure 2 illustrates the order of study procedures and stratification factors.

Page 4 of 20 Revised: May 25, 2018

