Covariates. Controlling for covariates is an important part of any analysis. While randomization and stratification should remove effects of these variables, additional statistical control curtails potential unhappy randomizations and other threats to internal validity. As such, we will examine differences between experimental conditions for the following variables: non-verbal cognitive skills, degree of hearing loss in the better ear, hearing age, hours of hearing device use, SES, sign exposure in the home, other spoken languages in the home and amount of community-based early intervention therapy services. Should a difference exist at any point in the study, we will include that variable in all statistical analyses.

Multiple testing. Our proposed analyses and rich multivariate data collection will allow us to test hypotheses in multiple ways. Our focus on SEM will allow for complex hypotheses to be tested with a single model, obviating part of the need for multiple testing corrections. However, we will further employ Benjamini-Hochberg corrections⁸⁸ as needed to correct for multiple testing. This procedure is a more sophisticated alternative to traditional Bonferroni corrections that better account for multiple simultaneous significant parameters.

[figure not shown]
Aim 1 Analyses

This aim tests the main effects of the intervention, both on parental use of communication support strategies and on child prelinguistic skills. We predict that: (a) parents in the intervention group will use more communication support strategies during intervention than parents in the control group (analysis 1.1); (b) children in the intervention group will have greater growth in rate of prelinguistic communicative acts between 12 months (pre) and 18 months of age (post) (analysis 1.2a) and greater overall prelinguistic skills at 18 months of age (post) (analysis 1.2b) than children in the control group. We will employ a mix of traditional and advanced statistical methods, balancing simplicity of linear regression and related methods with sophisticated SEMs that handle attrition and missing data and allow for more flexible integration of time-varying covariates.

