One example of a latent growth curve model is shown in Figure 2, where latent intercepts (level) and slopes (indicated by the circles labeled " L_c " and " S_c ") represent unmeasured variables that describe how children differ from each other in their overall level of prelinguistic development. These two latent variables predict and describe how children grow in their prelinguistic communicative abilities from age 12 months (C_{12}) to age 18 months (C_{18}). Latent growth models will be used for analyses 1.1 and 1.2a, all of which use a slope factor as a dependent variable.

Aim 1 analytic plan. Analyses for Aim 1 will utilize SEM equivalencies of both traditional regressions and growth curve extensions of these models. We will estimate all models in SEM to minimize the impact of attrition.

Analysis 1.1. Intervention will predict the slope factor in a latent growth curve model of overall parent use of communication support strategies, which is a latent variable of parent use of communication support strategies estimated monthly from 12 months (pre) to 18 months of age (post). This will utilize the CUFFS method (McArdle, 1988) of estimating growth in latent variables.

Analysis 1.2a. Intervention will predict the slope factor in a latent growth curve model of child prelinguistic communicative acts from a language sample from 12 months (pre) to 18 months of age (post). This will be accomplished by including intervention as a predictor in the child prelinguistic communicative acts growth curve.

Analysis 1.2b. CSBS Total Scaled Scores at 18 months of age (post) will be regressed on intervention status controlling for CSBS Total Scaled Scores at pre-test and other relevant covariates.

Aim 2 Analyses

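### The two randomisation stratification factors are not prespecified as covariates in any SAP model, which may forgo precision and make the tests conservative

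*SAP*

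**What the plan says.** Protocol 8.0 (Procedures Involved): "Randomization will be stratified by hearing device status (hearing aid or bone conduction device, cochlear implant) and communication mode". Communication mode has two levels, spoken only and sign plus spoken. Dyads are randomised after both factors have been determined, so the strata are known for everyone randomised.

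The SAP's Covariates paragraph names eight variables to be compared between arms. The list begins "we will examine differences between experimental conditions for the following variables: non-verbal cognitive skills, degree of hearing loss in the better ear, hearing age", continues "hours of hearing device use, SES, sign exposure in the home, other spoken languages in the home", and ends with the amount of community early intervention services. The entry rule is "Should a difference exist at any point in the study, we will include that variable in all statistical analyses". Neither stratification factor is on the list.

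The individual analyses specify the following:

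- **1.2b** regresses post-test CSBS on intervention, "controlling for CSBS Total Scaled Scores at pre-test and other relevant covariates". The other covariates are not defined. 3.2b controls for pre-test in the same manner as 1.2b.
- **1.2a** names intervention only: "This will be accomplished by including intervention as a predictor in the child prelinguistic communicative acts growth curve". The entries for 1.1, 3.1 and 3.2a likewise name no covariates.
- **Aim 4** refers to relevant covariates at each mediation step, again undefined.

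The Power Analysis section assumes control for pre-test and does not mention the strata.

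**The concern.** Balanced allocation within strata removes between-stratum variation from the true sampling variance of the arm comparison. A model without the strata still counts that variation as residual noise. Its reported standard error is then larger than the true one, its intervals are too wide and its test rejects too rarely under the null. This happens only to the extent that the strata predict the outcome after pre-test is accounted for.

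The SAP's selection rule does not repair this, because it looks for imbalance. Prognostic strength is the reason to adjust for a stratification factor, and the rule does not consider it.

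At stake are precision in the intervention comparisons and a fixed adjustment set. While the covariates remain undefined, whether the strata go in can be decided after the data are seen.

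**Working it through.** **Inputs from the SAP Power Analysis section.** 96 recruited, 10% attrition, 86 analysed. 80% power for d=.61 and 90% for d=.71 at n=86; d=.58 and d=.67 at n=96. Control for pre-test.

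**Assumed, because the documents do not state them.** Two-sided alpha of .05; 1:1 allocation; the share R of residual variance (after pre-test) explained by the two strata, taken as 0 to 20%.

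**Step 1: reproduce the stated power.** Noncentral t with one covariate (df = n − 3):

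- n=86: d=.61 gives 79.8%, d=.71 gives 90.2%, d=1.07 gives 99.8%.
- n=96: d=.58 gives 80.3%, d=.67 gives 90.1%.

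The 80%-power effect at n=86 solves to .611. A one-sided .05 test would give .54, so the two-sided assumption fits. The plan's figures therefore reproduce with no credit taken for the strata.

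**Step 2: effect of R.** With exact balance within strata:

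- reported SE / true SE = 1/√(1 − R)
- true two-sided type I error ≈ 2[1 − Φ(1.96/√(1 − R))]
- adjusted 80%-power effect ≈ .611 × √(1 − R), with df = n − 5 (pre-test plus two binary strata)

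| R | SE excess if strata omitted | Type I error, formula | 80%-power d, adjusted | Power at d=.61, adjusted |
|---|---|---|---|---|
| 0% | 0% | 5.0% | .61 | 79.8% |
| 5% | 2.6% | 4.4% | .60 | 81.8% |
| 10% | 5.4% | 3.9% | .58 | 83.8% |
| 20% | 11.8% | 2.8% | .55 | 87.8% |

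For example, at R=10%: 1/√.90 = 1.054 and .611 × √.90 = .580.

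**Step 3: simulation without exact balance.** 6,000 trials per setting at n=86, using permuted blocks of 4 within the four cells, 30% cochlear implant and 30% sign plus spoken (block size and shares assumed).

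| R | Mean reported SE / true SE, strata omitted (null) | Type I error, strata omitted | Power at d=.61, omitted | Power at d=.61, adjusted |
|---|---|---|---|---|
| 0% | .2159 / .2149 | 4.6% | 79.7% | 79.5% |
| 5% | .2159 / .2104 | 4.1% | 79.7% | 81.3% |
| 10% | .2163 / .2069 | 3.9% | 81.5% | 84.2% |
| 20% | .2163 / .1959 | 3.3% | 81.8% | 87.7% |

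The simulation follows the formula but is milder at R=20%: the SE ratio is .2163/.1959 = 1.104 against 1.118, and type I error is 3.3% against 2.8%. Unfilled blocks leave some imbalance. A fair statement is about 3%.

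**Scale.** The SAP says that losing nobody to attrition would move the 80%-power effect from .61 to .58. Adjustment at R=10% gives the same gain, since 86/.90 = 95.6, close to 96.

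**Coverage.** These figures apply to regressions 1.2b and 3.2b. Analyses 1.1, 1.2a, 3.1 and 3.2a test an intervention effect on a growth slope and have a separate simulation-based power statement. Omission matters in the same direction there if the strata predict slope, but the documents give too little to compute a size.

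**The case against.** **The strata may still enter.** A reader might infer that they are left out of every model. The documents do not go that far. The open covariate terms in 1.2b and Aim 4 could include them, the Missing data paragraph adds predictors of missingness as covariates, and nothing excludes them. This stands: the accurate statement is that they are not prespecified. However, an undefined term does not guarantee inclusion, and the only stated selection rule is the difference-triggered one.

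**The SAP favours adjustment.** A reader might take "While randomization and stratification should remove effects of these variables" to mean that the SAP thinks stratification makes adjustment unnecessary. The rest of that sentence argues for additional statistical control as protection against chance imbalance, so that reading fails. What remains is narrower: the stated reason for adjusting is imbalance, and precision is not mentioned.

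**Related variables are listed.** Sign exposure, degree of hearing loss and hours of device use plausibly overlap with the strata. This makes the loss less certain. They are still different variables, and they enter only if the arms differ.

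**The size is assumed.** This stands in full. At R=0 nothing is lost, and no document figure supports any particular R.

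**Validity is not threatened.** This also stands. A reader might infer that the power statement fails or that the estimate is biased. Neither follows: d=.61 reproduces without the strata, and omission makes the test conservative.

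**Conclusion.** The concern holds as a gap in prespecification with a possible cost in efficiency. The factors that structure the randomisation are not named in any model, and the stated rule would seldom bring them in. In 1.2b and 3.2b the cost runs from nothing (R=0) to a standard error about 12% too large and a type I error near 3% (R=20%). It rests on the assumed R, 1:1 allocation, two-sided .05 and reasonably tight balance within strata; the documents do not describe the blocking. That the strata are unspecified is certain from the text, whereas the size of the loss is not. The direction favours adjusting: if the strata are not prognostic, adjustment costs almost nothing (simulated power 79.5% against 79.7%). The change is worth making, but the planned tests are not invalid without it.

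**What to change.** State in the SAP that hearing device stratum and communication mode stratum enter every intervention-effect model in Aims 1 to 3 as fixed covariates, regardless of observed balance. In the growth models they should act on both the intercept and slope factors. Use the strata as recorded at randomisation: Protocol 8.0 places cochlear implant candidates, and children with one hearing aid and one implant, in the implant stratum, so device worn is not an exact substitute. In the same edit, define the other covariates allowed in 1.2b.

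The cost is a sentence or two in the SAP and two degrees of freedom per model (two per growth factor in the growth models). No new data are needed.
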